Our team has a unique opportunity to leverage and build on existing data and ongoing relationships with a network of motivated ICUs and the Society of Critical Care Medicine. Our team recently partnered with the SCCM to create the "ICU Liberation Collaborative," a QI project to foster the bedside application of the PAD Guidelines through wide-scale dissemination and implementation of the ABCDEF bundle.^{6,27} The Collaborative was led by an internationally recognized, multidisciplinary group with expertise in bundle-related clinical trials, implementation and dissemination research, and large-scale QI efforts. These experts operationally defined the new ABCDEF bundle. The SCCM provided overall project management, and each regional collaborative was led by a team including a registered nurse (RN), medical doctor (MD), respiratory therapist (RT), physical/occupational therapist (PT/OT), and pharmacist to mirror the interprofessionalism implicit in the bundle. The Collaborative included 68 ICUs from academic, community, and Veterans Affairs (VA) hospitals located

throughout the United States. Guided by the Consolidated Framework for Implementation Research (CFIR),⁴⁴ the Collaborative formally ran from August 2015 to April 2017.

Collaborative participants were required to attend four in-person meetings, monthly co-learning calls, and database training sessions. They were also invited to participate in a listserv and select in-person site visits. All teams submitted bundle-related performance and outcome data and completed pre- and post-implementation questionnaires focused on assessment of teamwork, work environment, overall ICU care, and organizational structure (see **APPROACH**).

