β_{1j} Month + β_{2j} Imp + β_{3j} Month * Imp + e_{ij} , where (1) Logit(Y_{ij}) denotes the logit (or log-odds) of receiving bundle performance for the i^{th} ICU-day of the j^{th} patient; (2) Month is the month indicator of the study period (a total of 20 months coded as -5 to 0 for pre-implementation period and 1 to 14 for implementation period); and (3) Imp denotes an indicator variable coded as 0 for pre-implementation period and 1 for the implementation period. Therefore, Logit(Y_{ij}) is modeled as a linear function of $\beta_{0j} + \beta_{1j}$ Month for the pre-implementation period and $(\beta_{0j} + \beta_{2j}) + (\beta_{1j} + \beta_{3j})$ Month for the implementation period. β_{2j} and β_{3j} are the estimates of level and slope changes due to the intervention implementation. A significant level change (β_{2j}) indicates an immediate change in the level of bundle performance at the initiation of intervention implementation. A significant slope change (β_{3j}) indicates different trends over time during the pre- vs. post-implementation periods. Under the multilevel modeling framework, level-2 models will fit β_{0j} , β_{1j} , β_{2j} , and β_{3j} each as a linear function of fixed-effects of patient characteristics and patient-specific random effects. The patient-specific random terms allow for adjustment of within-patient clustering of ICU-days. Take patient gender as an example. From the combined multilevel segmented logistic regression model, we will (1) estimate the overall trends during the pre- and implementation periods (solid black lines); (2) derive fixed-effect estimates by patient characteristics (Figure 4, long dashed line and short dashed line for each gender); (3) test the significance of hypothesized subgroup differences (e.g., older age, obese, and non-English speaking) in the these estimates; and (4) include patient-specific random terms to allow for variability by patients (patient-specific lines not shown in Figure 4). The model can be simplified if supported by the preliminary results. For example, if the initial analyses for an outcome (e.g., element E performance) suggest that (1) there are no significant level change and slope change for both male and female patients and (2) the overall increasing trend over time does not differ by patient gender, we can reduce the model to a parsimonious form using multilevel logistic regression to model the probability of having an outcome as a function of fixed effect of patient gender, fixed effect of time, and patient-specific random effects. We can also further extend the model to (1) include multiple patient characteristics simultaneously in the model to generate multivariable adjusted estimates, (2) perform curve fitting for linear or non-linear trend, and (3) adjust for additional clustering (e.g., within-organization clustering). The above desried multilevel segmented logistic regression approach will be applied to analyzing complete and element bundle performance measures. For proportional bundle performance, we will use multilevel segmented Poisson regression instead.

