Missing data. Data for Aim1 have a relatively low rate of missing (< 5%). We will primarily report data from complete cases without data imputation. As a sensitivity analysis, we will examine the pattern of missingness and repeat the analyses with multiple imputation.

Aim 2: Examine unit-level variation in ABCDEF bundle adoption and associated provider- and organization-level characteristics.

Design and Rationale. In Aim 2, we will use existing SCCM ICU Liberation Collaborative data to examine unit-level variation in ABCDEF bundle adoption and associated provider- and organization-level characteristics. Myriad provider- and organization-level characteristics are believed to affect delivery of the bundle.^{35,40,124-126,128} However, there is little evidence outlining which, and to what degree, these characteristics affect bundle performance. Given significant financial pressure, hospitals are seeking a “silver bullet” to reduce the iatrogenic risks associated with prolonged MV, delirium, and ICU-acquired weakness. Completion of this aim would advance knowledge by identifying provider- and organization-level characteristics amenable to implementation interventions.

Setting and Sample. We will use provider- and organization-level data from two discrete surveys administered before and after the Collaborative. All full- and part-time nurses (RNs and Advanced Practice), MDs (residents, fellows, and attending), respiratory therapists, pharmacists, PT/OTs, nursing assistants, case managers, and other health care providers practicing in an ICU participating in the Collaborative were **eligible** to participate in the first survey, “Interprofessional ICU Team Survey.” The second survey, “Organizational Survey,” was **completed** jointly by the nursing and medical director of a participating ICU. In total, 7,307 ICU providers (5472 pre; 3247 post) completed the Interprofessional ICU Team Survey. Organizational surveys were completed by the nursing and medical directors of all 68 ICUs.

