The **Organizational Survey** collected information on (1) hospital and ICU characteristics, (2) utilization rates, (3) ICU staffing patterns, (4) ICU organization, and (5) ICU rounding and ABCDEF bundle practices. The first section contains questions on characteristics of the **hospital** (i.e., type, locale, teaching status) and **ICU** (i.e., type, training programs). The next section contains questions focused on **utilization data**, such as total number of hospital, ICU, and step-down beds, and number of annual hospital and ICU admissions. The third section collects ICU MD, advanced practice provider, RN, and additional ICU team member **staffing, education, and certification data**. The fourth section has questions on the **organization of the ICU**, such as whether it is an open, semi-open, or closed unit, and if the ICU has a medical and/or nursing director. The final section has questions regarding **ICU rounding and ABCDEF practices**. This section collects specific data regarding the use of daily rounds, where rounds are performed, who regularly attends rounds, use of PAD assessment tools, which protocols and teamwork tools the ICU uses, and types of QI experience. This survey was completed by both the nursing and medical director of a participating Collaborative team. The Organizational Survey is being used as proxy measure for the CFIR's construct "inner setting" domains of structural characteristics, networks and communication, culture, implementation climate, readiness for implementation. This survey also relates to the CFIR's "process" domains of planning and engaging.

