Data Analysis. The overall analytic strategy for Aim 2 will be the same as described for Aim 1. That is, using multilevel segmented logistic regression modeling for complete and element bundle performance and multilevel segmented Poisson regression for proportional performance. First, we will examine the variation across ICUs in bundle performance by adding ICU-specific random effects to the model. All significant patient-level characteristics from Aim 1 will remain in the model as covariates so that ICU-level estimates are risk-adjusted for patient case mix. From the model, we can (1) quantify the degree of ICU variation using the intra-class correlation (ICC); (2) derive the ICU-specific adjusted rates of bundle performance at the last month of implementation and examine their distribution (mean, variance, median, interquartile range, and range); and (3) rank the ICU-specific adjusted rates from low to high and identify the top 5 and bottom 5 ICUs with best and worst adjusted performance rates. Next, we will estimate the effects of organizational characteristic on bundle adoption by adding them as fixed effects to the model. Organizational survey at the post-implementation period will be estimated as fixed effects to model the level change (β_{2j}) and slope change (β_{3j}). While data from the pre-implementation period will be estimated as fixed effects to model pre-implementation level (β_{0j}), pre-implementation slope (β_{1j}), post-implementation level change (β_{2j}), and slope change (β_{3j}) (see **Data Analysis section for Aim 1**). Again, multilevel clustering (within-patient clustering of ICU days and within-ICU clustering of patients) will be adjusted in the model using random effects terms. As the provider-level data can be linked to specific ICUs, but not linkable to specific patient and patient ICU days, we will use multilevel modeling (level-1: time-point [pre- and post-survey], level-2: provider; level-3: ICU) to model the fixed effect of time, provider-level assessments (AITCS, HWEA,^{136,137} and ICU Care and Perceptions surveys), and their interactions on ICU-level adjusted performance rates. From the model, we can derive contrast estimates on the effect of change in

provider-level assessments on ICU-level bundle adoption. We will also extend the model to adjust for ICU-within-organization clustering.

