Missing data. All 68 ICUs before and 42 ICUs after the Collaborative completed the organizational survey. The advantages of the multilevel model for analyzing longitudinal data lie in its flexibility in handling missing data and more efficient use of available data. Multilevel modeling allows for varying numbers of waves of data per study unit; the same number of waves of data is not required for all hospitals. Thus, missing data will be more easily managed, and all available data will be used for model estimates. Nonetheless, we will carefully examine the extent and pattern of missing data and impute missing values when appropriate. If missing not at random exists, we will use pattern-mixture modeling. We will also conduct sensitivity analyses to examine the robustness of study findings with and without multiple imputation or using pattern-mixture modeling.

Aim 3: Determine which implementation strategies result in the greatest adoption of the ABCDEF bundle.

Design and Rationale. Identifying feasible and effective ABCDEF bundle implementation strategies that are contextually appropriate remains a challenge for ICU researchers and practicing clinicians. In Aim 3, we will extend data collection and use both quantitative and qualitative approaches (i.e., using an online survey, concept mapping exercise, and an expert panel) to gain a deeper understanding of which implementation strategies are most likely to overcome barriers to ABCDEF bundle adoption.

Setting and Sample. Healthcare providers from the 68 sites that participated in the ICU Liberation Collaborative will be included in the work outlined in Specific Aim 3. These healthcare providers will have experience working in one of the ICU Liberation Collaborative units and come from various professional groups (e.g., nursing, medicine, pharmacy, physical/occupational/respiratory therapy). We will also include a subgroup of 10-12 healthcare providers who currently serve of the SCCM's ICU Liberation and/or Quality and Safety committee and two members of the SCCM's Council who are responsible for overseeing the society's quality & safety initiatives in an expert panel.

Procedures and Data Sources.

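### Aim 2 lets an organizational survey taken after the Collaborative explain the shift at its start: for changeable items the answer may be a result of adoption, 26 of 68 ICUs lack it, and no survey wave is named primary

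*Combined protocol and SAP*

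**What the plan says.** Aim 2, Data Analysis gives the Organizational Survey two roles. For the wave after the Collaborative: "Organizational survey at the post-implementation period will be estimated as fixed effects to model the level change" (β2) and also the slope change (β3). For the wave before it: "While data from the pre-implementation period will be estimated as fixed effects to model pre-implementation level", and in the same sentence the pre-implementation slope, the level change and the slope change. The section does not say whether the two waves enter together or in separate models, or which one carries the Aim 2 conclusion.

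Aim 1, Data analysis, whose model Aim 2 reuses, says that a significant level change "indicates an immediate change in the level of bundle performance at the initiation of intervention implementation".

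On timing, Aim 2, Setting and Sample refers to "two discrete surveys administered before and after the Collaborative". Preliminary Data states that "the Collaborative formally ran from August 2015 to April 2017". Aim 1, Procedures and Data Sources puts baseline data at January to June 2015 and implementation data at January 2016 to March 2017.

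On content, Aim 2, Measures lists five survey sections. The fifth covers rounding and bundle practices and includes "use of PAD assessment tools, which protocols and teamwork tools the ICU uses".

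On completeness, Aim 2, Missing data reports: "All 68 ICUs before and 42 ICUs after the Collaborative completed the organizational survey".

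**The concern.** Aim 2 is meant to find organizational characteristics that implementation work could act upon, and the results are to shape strategies for a later cluster randomized trial. A characteristic can be proposed as a determinant of an early shift in performance only if it was in place when the shift occurred. The post survey records the unit as it stood after the whole outcome window.

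For features that the Collaborative set out to change, an ICU that adopted the bundle well would be expected to report more of them afterwards. Entered as a predictor of level or slope change, such an item can show a strong association even if it did nothing to bring adoption about. The items most exposed are also the ones most likely to be recommended as levers. The section on potential problems lists limitations for Aims 1 and 2 but does not mention this one.

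A second issue is that more than a third of the ICUs have no post survey, while the power statement rests on all 68.

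**Working it through.** **Time order.** The month variable is "coded as -5 to 0 for pre-implementation period and 1 to 14 for implementation period", and the model contains Month, Imp and Month × Imp. The two fitted lines are:

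- before: β0 + β1·Month
- during: (β0 + β2) + (β1 + β3)·Month

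Their difference at Month 0 is β2, so β2 is a jump at the boundary between the periods. The first month of implementation data is January 2016. The Collaborative ended in April 2017 and the post survey came after it. January 2016 to April 2017 is 15 months, so the predictor follows the jump by roughly that long. It also follows the whole of the slope that β3 describes.

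**Content.** By exposure to reversal, the survey sections divide as follows:

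- Little exposed: hospital type, locale, teaching status, ICU type. These rarely change over such a period, so a late reading is close to an early one.
- Possibly exposed: staffing and some features of unit organization.
- Most exposed: section 5 (rounding, assessment tools, protocols, teamwork tools, bundle practices). Aim 2, Procedures says the Collaborative's meetings and calls taught teamwork and the tools for it.

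**Missing post surveys.** 68 − 42 = 26 ICUs; 26/68 = 38.2% lack the survey and 42/68 = 61.8% have it.

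**Detectable effects.** Aim 2, Sample Size/Power Analysis states 80% power for an odds ratio of 1.80 on level change and 2.96 on slope change, for a site-level factor split 20:80. These come from a simulation whose inputs are not fully reported, so they cannot be reproduced. The closed-form figure in the same paragraph can be: Spearman-Brown gives n = 0.8 × 0.7 / (0.3 × 0.2) = 9.33, rounded up to the stated 10. That figure concerns the reliability of ICU rates and does not bear on this point.

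Take the stated odds ratios as correct for 68 ICUs, and assume complete-case analysis with standard error proportional to 1/sqrt(ICUs):

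- sqrt(68/42) = 1.272
- level: exp(1.272 × ln 1.80) = 2.11
- slope: exp(1.272 × ln 2.96) = 3.98
- implied standard error for level with 68 ICUs: ln 1.80 / (1.960 + 0.842) = 0.210; with 42 ICUs, 0.210 × 1.272 = 0.267
- power at 1.80 with 42 ICUs: Φ(0.588/0.267 − 1.960) ≈ 0.60; the same calculation at 2.96 also gives about 0.60
- the 20:80 split becomes about 8 against 34 ICUs, instead of about 14 against 54

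**Illustration of reversal.** Suppose a characteristic has no effect on adoption, but adoption drives the post-survey answer, with correlation ρ between that answer and the ICU's level change. Power from Fisher's z with 42 ICUs is Φ(atanh(ρ)·sqrt(39) − 1.960), plus a negligible opposite tail. The values of ρ are assumed, not taken from the documents.

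| ρ | chance of p < 0.05 |
|---|---|
| 0.1 | 10% |
| 0.2 | 25% |
| 0.3 | 49% |
| 0.4 | 75% |
| 0.5 | 93% |

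**The case against.** The strongest reply is that the plan already contains a correctly timed analysis: the pre survey, complete for all 68 ICUs, also models level and slope change. That stands. A reader who stops at the sentence on the post survey might infer that Aim 2 explains the level change only with a later measurement; the next sentence shows otherwise. It does not settle the matter, because the role of each wave is left open. If both enter one model, the post value can absorb the effect of the earlier one. If they enter separately, two answers may conflict and there is no rule for choosing.

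A reader might also infer that the post survey is the outcome measured a second time, so that the whole analysis is circular. The documents do not support this. Performance is coded per ICU-day from medical record review, whereas the survey describes unit arrangements, and much of it is stable. Nor do the documents date when protocols were introduced: one adopted early in the Collaborative could be a genuine cause. Reverse causation is therefore an inference from survey content and the Collaborative's aims.

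Third, the estimated level change spans the interval from June 2015 to January 2016, five months of which (August to December 2015) fall within the Collaborative. Changes made then could contribute to β2, and only a later survey could record them. This stands as a cost of relying on the pre survey.

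Fourth, Aim 2, Missing data plans imputation where suitable, pattern-mixture models and sensitivity analyses, so loss of 26 ICUs is not certain. That stands too. However, its argument that multilevel models accept unequal numbers of survey waves concerns repeated measurements; it does not supply an ICU-level covariate that was never collected. None of these methods repairs time order.

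**Conclusion.** The point holds for the post survey's changeable items, chiefly section 5. Their coefficients on level and slope change cannot be read as determinants of adoption, because the survey follows both. The lag behind the level change is roughly 15 months, an estimate because the survey date is not given. For stable items the timing matters little. The pre-survey analysis is sound in time order and complete, but the plan does not give it priority.

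If the 26 ICUs without a post survey are dropped, detectable odds ratios rise from 1.80 to about 2.11 and from 2.96 to about 3.98, with power near 60% at the stated values. This rests on taking the stated odds ratios as correct, on no imputation, and on standard errors scaling with 1/sqrt(ICUs). Successful imputation would make the loss smaller, so these are complete-case figures, not a forecast. How often reversal would produce a false finding cannot be determined from the documents; the correlation table only shows how sensitive the test would be.

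**What to change.** In Aim 2, Data Analysis:

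1. Name the pre-Collaborative Organizational Survey (68 of 68 ICUs) as the primary source of organizational predictors for level change and slope change, and do not enter post-survey values in the same model.
2. Do not use post-survey section 5 items as predictors of bundle performance. Report them descriptively, or analyse their pre-to-post change as an outcome.
3. Report any other post-survey associations as exploratory, with the number of ICUs contributing to each.

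In Aim 2, Missing data, say how an absent post survey is handled as a missing ICU-level covariate. Also reconcile the count of 42 with Preliminary Data, which says all teams completed questionnaires before and after, and with Setting and Sample, which reports organizational surveys for all 68 ICUs without naming the wave.

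The cost is wording; no new data are needed. The real loss is that organizational features introduced during the Collaborative, including those from August 2015 to January 2016, are then reported only as exploratory or descriptive.

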Our preliminary data also show that collaborative participation resulted in significant but highly variable ABCDEF bundle adoption. Our next goal was to determine if collaborative participation led to increased bundle adoption. We were interested in exploring if some sites were "better" ABCDEF bundle adopters than others. The presence of a substantial amount of variability in our data would present us the opportunity to learn both from high- and low-bundle-performing sites. We calculated monthly rates of complete bundle performance, proportional bundle performance, and element-specific performance for the 17,258 patients across 49,109 full ICU days. We used segmented regression analysis for interrupted time series data to model the linear trend of bundle performance rates as a function of time for each segment (1-6 months pre-Collaborative involvement and 7-20 months during the Collaborative).

Complete bundle performance levels were low in the baseline (pre-Collaborative) period (i.e., < 4%). Complete bundle performance increased 2.0% (SE = 0.9%, $P = 0.057$) immediately after joining the Collaborative, and each month was associated with 0.6% greater increase (SE = 0.2%, $P = 0.038$) in complete bundle performance rates, compared to a relatively flat trend in the pre-Collaborative period. Proportional bundle performance rates also significantly increased by 3.8% (SE = 1.6%, $P = 0.026$) immediately after joining the Collaborative, then increased monthly at the same speed as the trend in the pre-Collaborative period (2%, SE = 0.4%, $P = 0.57$).

Bundle performance was highly variable among ICUs and across individual bundle elements; interquartile ranges of > 20% existed for all performance measures. (**Figure 1**) Elements A, C, D, and F were performed on average $\geq 70\%$ of the time at the end of the Collaborative:

Figure 1. Variation among ICUs in Unadjusted ABCDEF Bundle Performance Rates

adoption of elements B1, B2, and E (SATs, SBTs, and early mobility) proved far more challenging. For example, at the end of the Collaborative, an average $\leq 40\%$ of patients participated in early mobility and less than half of patients requiring MV received a daily SBT. Although overall performance was relatively poor, there were indeed some very good bundle performers.

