Local staff who attended a training webinar and as-needed support from SCCM managers entered de-identified data into the collaborative database at their individual hospitals. Data were collected retrospectively during a 6-month baseline period (January 2015-June 2015) and prospectively during a 14-month implementation period (January 2016-March 2017). During the baseline (pre-Collaborative) period, staff from each site entered data on the first 5 consecutively admitted ICU patients each month (30 baseline patients per site). Throughout the implementation period, site staff collected data on the first 15 consecutively admitted patients per month. For each patient, daily data were collected for a maximum of seven ICU days (average of 3.3 ICU-days per patient) or until patients transferred out of the ICU, were designated non-ICU status, or died.

Measures. Patient-level variables include: age, sex, race, ethnicity, language, body mass index (BMI), admitting diagnosis, severity of illness, and preadmission residence and mobility status. The severity of illness scores collected in the Collaborative included the Acute Physiology and Chronic Health Evaluation (APACHE) II,¹³⁰ APACHE III,¹³¹ and APACHE IV¹³² referent to the patient's status at the time of ICU admission.

Data analysis. We will conduct similar analyses for each of the performance measures (performed vs. not performed), including complete, proportional, and each element performance. We will first use descriptive statistics to examine data distribution, check for outliers, and summarize patient characteristics. Bivariate tests (e.g., *t* test or Chi-square statistics) will be used to compare patient characteristics in the pre-Collaborative and Collaborative periods.

Using multilevel segmented logistic regression modeling for interrupted time series data, we can model the likelihood of bundle performance change over time, both before and during the periods of Collaborative implementation. **Figure 2** shows a hypothetical example. The basic form of the level-1 model (Figure x, solid black line) can be written as $\text{Logit}(Y_{ij}) = \beta_{0j} +$

Figure 2. Segmented logistic regression for ITS data-A hypothetical example

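### Aim 2's provider-survey model regresses an outcome shared by a whole ICU on individual scores, so it gives either no estimate or too many false positives

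*Combined protocol and SAP*

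**What the plan says.** The Aim 2 Data Analysis section notes that survey responses can be tied to an ICU but not to patients or ICU-days. It therefore uses a separate model with levels "level-1: time-point [pre- and post-survey], level-2: provider; level-3: ICU". The fixed effects are time, the three provider instruments (AITCS, HWEA, ICU Care and Perceptions) "and their interactions on ICU-level adjusted performance rates". The stated product is: "From the model, we can derive contrast estimates on the effect of change in" provider assessments on adoption in the ICU. The one further clustering term offered is ICU within organization, which lies above the ICU.

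The same section defines an ICU-specific adjusted rate once, where it says the model can "derive the ICU-specific adjusted rates of bundle performance at the last month of implementation". It does not say which rate the provider model uses at the pre-survey, or which random terms it contains. The Aim 1 Data analysis section, whose strategy Aim 2 adopts for the patient-day models, fits the four segmented coefficients "each as a linear function of fixed-effects of patient characteristics and patient-specific random effects".

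Aim 2 Setting and Sample reports 5,472 pre and 3,247 post responses from 7,307 providers. On the separate organizational survey, Aim 2 Missing data says: "All 68 ICUs before and 42 ICUs after the Collaborative completed the organizational survey".

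**The concern.** The predictors vary between respondents and the outcome does not. Naming the ICU as a level does not create outcome variation within it. Depending on how the unstated parts are filled in, the model either has nothing left to explain or counts one ICU-by-wave value as if each respondent had supplied it independently.

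This is Aim 2's only analysis of provider-level characteristics, and the Approach section says the results will shape strategies for a later cluster randomized trial. The risk is that the promised contrast cannot be produced, or that a chance score-by-time interaction is reported as a driver of adoption. The ICU ranking, the ICC and the organizational-characteristic models are not affected.

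**Working it through.** **The plan's own figure.** Aim 2 Sample Size/Power gives 10 as the minimum sample per ICU for reliability 0.8 at ICC 0.3. Spearman-Brown: 0.8 × 0.7 / (0.3 × 0.2) = 9.33, rounded up to 10. It reproduces, but it concerns the reliability of one ICU's rate. The plan gives no power or precision figure for the provider model.

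**Inputs from the documents.** Responses: 5,472 + 3,247 = 8,719. Per ICU: 5,472/68 ≈ 80 pre and 3,247/68 ≈ 48 post. The team survey's post-wave ICU count is not given. Borrowing the organizational survey's 42 as a sensitivity value gives 3,247/42 ≈ 77 post. Two-sided 5% is the level stated for the Aim 1 power work.

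**Assumed.** Score ICC 0 to 0.10, and pre-post correlation of ICU rates 0.5.

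**Reading (a): one rate per ICU.** The 8,719 rows hold 68 distinct outcome values. In a trial fit with an ICU intercept, the largest within-ICU deviation of the outcome was 2e-16. The time, score and interaction coefficients were about 1e-14 and the residual variance about 3e-13. The likelihood grows without bound as the residual variance goes to zero, so the contrast is not estimable.

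**Reading (b): one rate per ICU and wave, random intercepts only.** There are 2 × 68 = 136 distinct values and no variation within an ICU-wave. The ICU intercept absorbs stable ICU differences but not the ICU-by-wave error. Score-by-time rejection with the outcome unrelated to scores (REML, time centred, 2,000 datasets per setting; 300 for the last row):

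| Persistent score ICC | 0 | 0.005 | 0.02 | 0.05 | 0.10 |
|---|---|---|---|---|---|
| 68 ICUs, 80 pre and 48 post | 8% | 16% | 31% | 48% | 61% |
| Post responses from 42 ICUs only | – | 17% | 37% | 53% | 65% |
| Provider intercept added, 21 linked respondents per ICU | – | 19% | 31% | 52% | 58% |

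- A second set of runs (800 to 1,000 per setting) gave 23% at ICC 0.01, 47–50% at 0.05 and 56–60% at 0.10.
- The pre-post correlation matters little. With persistent and ICU-by-wave score ICCs both 0.05, rejection was 57%, 53% and 56% at correlations 0.3, 0.5 and 0.8.
- ICU-based degrees of freedom (66 or 40) still gave 30–35% at ICC 0.02.
- In a model with no interaction, the overall score effect stayed at 5–6% under persistent clustering. It rose to 18–22% once scores also shared ICU-by-wave variation of 0.02.
- A design-effect check on that main effect uses 8,719/136 = 64.1 rows per ICU-wave. At ICU-by-wave ICC 0.01, 1 + 63.1 × 0.01 = 1.63, and 1.96/√1.63 = 1.53 implies 12%. At 0.05 the design effect is 4.16 and the implied rate 34%. Simulation gave 12–13% and 32–37%.
- ICU-level regression of change in rate on change in mean score rejected in about 4–7% throughout.

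**Reading (c): one rate per ICU and wave, with random level and change terms moved from the patient (Aim 1) to the ICU.** Two random terms per ICU fit its two values exactly. Within-ICU-by-wave outcome variance is zero (about 1e-30), and the model is degenerate again.

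**Query only.** 8,719 − 7,307 = 1,412 suggests that some respondents were matched across waves, yet the survey is described as anonymous.

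**The case against.** *The wrong contrast.* The 16–61% figures are for score-by-time. A within-ICU effect of change may be nearer the overall score effect, which is close to nominal in a model without interactions. This is true of that model, but the plan specifies interactions. In the interaction model the slope averaged over waves rejected in 9–12% and the post-wave slope in 21–47% (500 runs per setting, ICC 0.005 to 0.10). The size therefore depends on the contrast, but no contrast examined in the specified model keeps its level.

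*Reading (a) is uncharitable.* The last-month rate appears in a list about variation between ICUs, and the pre/post level implies a rate for each wave, which the segmented model could supply. That is fair, but the plan never says so, and supplying the rate leads to reading (b).

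*Reading (c) is an extrapolation.* This stands: the Aim 1 sentence concerns patient-specific terms, and nothing places them at ICU level in this model. It shows only that the natural repair of (b) also fails. ICU-clustered robust inference or aggregation is not excluded, but neither is planned.

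*The sizes are assumed, and the analysis is exploratory and uses existing data.* The first part stands and is why a range is shown. The second limits the consequences but does not make the model usable.

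**Conclusion.** The concern holds: the provider-survey model is wrong as written and must be fixed before analysis. With the only rate the plan defines, the effect-of-change contrast cannot be estimated. That conclusion is algebraic and rests on no assumed figure. With one rate per wave and random intercepts, the test is anti-conservative when scores cluster by ICU. Score-by-time false positives run from 16% at score ICC 0.005 to 61% at 0.10, against a nominal 5%. Those sizes rest on assumed score ICCs, roughly equal respondent numbers per ICU and an assumed pre-post correlation of ICU rates. Confidence in the exact size is moderate; confidence in the defect does not depend on it.

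**What to change.** In the Aim 2 Data Analysis section:

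1. Define the adjusted rate for each wave, list the random terms, and name the ICU as the unit of inference.
2. Aggregate each scale to an ICU-by-wave mean, weighted or shrunk for the number of respondents.
3. Then choose one of two forms. Either regress each ICU's change in adjusted rate on its change in mean score, or enter the ICU means as ICU-level fixed effects in the patient-day segmented model. The plan already handles organizational characteristics in the second way. ICU random effects on level and slope change should be written in explicitly.
4. Report the number of ICUs contributing to each wave and the score ICC. Treat the waves as repeated cross-sections unless a linkage key exists, and say whether one does.

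The second form suits complete performance better. Aim 1 Procedures and Data Sources gives "30 baseline patients per site" and 3.3 days per patient, so 30 × 3.3 = 99 baseline ICU-days per site. Preliminary Data states: "Complete bundle performance levels were low in the baseline (pre-Collaborative) period", with a figure below 4%, so fewer than 99 × 0.04 ≈ 4 complete-bundle days per ICU. A separate baseline rate for each ICU would be very imprecise.

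The cost is SAP wording and a simpler analysis of data already held. Intervals will be wider, and ICUs without post responses drop out of the change analysis. By Fisher's z at two-sided 5%, change-on-change has 80% power for a correlation of about 0.33 with 68 ICUs, or 0.42 with 42.
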